Asthma Self-Management: For asthma, self-management involves a number of tasks to prevent and manage symptoms, such as monitoring symptoms over time, avoiding known triggers, and taking medications properly. The Asthma Self-Management Questionnaire,⁷⁹ a newly developed measure recommended by experts convened for the Asthma Outcomes workshop,⁸⁰ includes 16 multiple-choice questions regarding knowledge of preventive strategies and controller medication use. Standardized scores (0-100) are generated, with higher scores indicating more knowledge of self-management. Cronbach’s alpha was 0.71. Wording of questions will be revised (e.g., “you” = “your child”) to be appropriate for parents of children with asthma.

Parental Self-efficacy: The Medical Competence Communication Scale (MCCS) measures patient’s perceptions of their own communication during their most recent medical visits.⁸¹ The patient version of the measure is used to assess information giving, seeking and verifying, as well as socio-emotional communication. The MCCS, patient version, consists of 23 items rated on a 5-point Likert scale (1= unimportant to 5= important) with a higher score indicating greater perception of communication competence. Cronbach’s alpha ranges from 0.76-0.92 on the various subscales. Only the 16 self-competence items will be administered in this study. Wording of questions will be modified to state “my child’s medical problem” rather than “my medical problem.” The Parent Asthma Management Self-Efficacy Scale (PAMSES) is a valid and reliable instrument designed to measure parent self-efficacy in preventing and managing children’s asthma attacks.⁸² The PAMSES consists of 13 items rated on a 5-point Likert scale (1=not at all sure to 5=completely sure) with a total possible score range of 13 to 65; higher scores indicate greater self-efficacy. Cronbach’s alpha in a sample of primarily White mothers was 0.87.⁸²

Parental Outcome Expectations: In accordance with other research of pediatric asthma interventions, to assess parents’ beliefs about possible asthma quality of life for their child we will administer an 8-item measure of parental expectations for asthma treatment.⁸³ Parents respond to statements about their expectations (e.g., “I believe that my child can be symptom free most of the time.”) using a 5-point Likert scale (1=strongly disagree to 5=strongly agree). Total scores are calculated by averaging across responses, and higher scores reflect more optimistic asthma outcome expectations (Cronbach’s alpha = 0.70).

Study Intervention

The T2B intervention will consist of a personalized, interactive text-messaging program with asthma and health communication education (derived from IMPACT DC and PEPAC), as well as follow-up reminders for scheduling asthma care appointments with PCP and annual flu vaccines. Participants randomized to the control group will also receive reminder texts to schedule with their child's PCP and to get an annual flu shot. An algorithm of text message delivery will be determined for each participant (see appendix for Sample Algorithm content). The manual/intervention protocol and text messaging content will be refined and finalized during the start-up phase of the project (see Protection of Human Subject section for timeline). Within 24 hours of enrolling in the study, participants in the intervention will begin receiving a series of automated bidirectional text messages to their mobile phones based on the education components of IMPACT DC and PEPAC. In order to be oriented and familiar with the content of these messages participants randomized to intervention will also receive face-to-face PEPAC education, including the 3S tool kit card during their baseline visit. Messages will originate from the T2B program during the first 3 months, after which parents can text key words to repeat or receive additional messages/education at any time.

Text messages will be individually tailored to include child and parent initials and, child's gender, Parents will also choose one goal important for improving management of their child's asthma and for communicating with their child's PCP regarding asthma care. A component of their text message communication education content will be based on their identified goal. Information for the tailored messaging will be collected as part of the baseline survey and will be verified and updated at the 3, and 6 month telephone interviews.

Two to three education messages will be sent each week for the first 3 months, one focused on an IMPACT DC asthma education message and a second on a PEPAC health communication message. Parents in our focus groups indicated that this frequency of messages would not be burdensome but welcomed and useful. Parents will also receive text message reminders to follow up with their child's PCP for asthma care at appropriate times based on the asthma care guidelines and relative to the date of the ED visit/enrollment into the program. Parents will also be prompted to reply to the text confirming a scheduled appointment with their child's PCP. Some messages will prompt participants to respond (e.g., key content questions, follow-up reminders for PCP visits, achievement of asthma management goals). Once a participant replies to a text message, the system will send a subsequent text message with appropriate feedback. The program will also allow participants to send a variety of keywords at any time to receive additional messaging. This will allow parents, for example, to request the 3 S's during a visit with the PCP. Other messages may include an embedded link to a URL with additional relevant content (e.g., videos demonstrating proper inhaler technique, explanation of controller vs. rescue inhalers), which we anticipate most participants will be able

to access on their mobile device given the majority of urban, low-income parents in a recent study owned smart phones.⁵⁹

Table 1. Text Message Healthcare Communication and Asthma Education Content

Theoretical Construct	Component of Intervention	Content	Week(s)
Outcome Expectations	Introduction to program	
 Welcome to Text2Breathe. As part of this study we will be sending you messages 2x/week over the next 4 months. (interactive) 	1-2
	Tailoring questions	
 Participant's initials, Child's initials, , Child's gender 	
	Identification of personal goals (tailored)	
 Fewer ED visits Missing less school Be more active Follow-up with PCP every 3 months 	
Facilitation	Education	
 2-3 messages/week – Personalized, Interactive Examples will be based on stated information and goals (personalized) Statement with response required about correct answer for example given (interactive) Asthma Education Example –Controller medications should be taken every day. Choose a time a day that you and [child's initials] will remember. Txt MEDS 4 info. Health Communication Example –Saying It Back is important 2 b sure you know your child's asthma plan. Txt 3SS for help on what to ask. 	3-12
	Reminder Messages	
 Reminder to follow-up with PCP, Influenza Vaccine Reminder Example –Time 4 [child's initials] 2 follow-up with PCP. Did u make an appt? Reply YES or NO. Reminder to schedule study follow up call 	
Self-efficacy	Keyword requests	
(3SS) –Info from communication toolkit (PCP) – Reminder of when to follow-up with PCP (GOAL) - Reminder of parent's intervention goals
 
(MEDS) – Info on difference between controller and rescue medications (TRIGGERS) – Info on common triggers
	13-52 or On demand

Participants will receive a handout with instructions on how to interact with the text message intervention (including opt-in instructions and numbers to call for problems). In addition, parents will be informed that the text messaging system is automated and their responses will be sent to a secured computer system so they should not send text messages seeking medical care. Should the participant send a text message to the system that does not align with the algorithm response programming, they will receive a standard message with instructions to contact the T2B team, their health care provider or 911 if it is an emergency. Research staff will also have the capacity to monitor participant engagement with the system to

troubleshoot any problems. Participants randomized to T2B, intervention, group will also receive a wallet sized “tool kit” reminding them of the 3 S’s and the key words to request text information.

REFERENCES CITED

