enhanced HC intervention to parents of children with other chronic conditions. In addition, the expedience of scaling up a text-message protocol means that our intervention can easily be adapted to reach a broader audience in a cost-effective manner when compared to ongoing face-to-face interventions. If efficacy is demonstrated, another next step will be to expand the program to other healthcare settings, such as primary care practices.

Study Design

We propose to conduct a RCT with low-income parents of children with physician-diagnosed asthma, ages 2-12 years inclusive, who are seen in the Seattle Children's or Mary Bridge Children's ED [for asthma care] to test the efficacy of our mHealth HC intervention, T2B, primarily for reducing ED/urgent care visits for asthma care. Each hypothesis will be tested by contrasting parents receiving T2B with parents receiving only standard ED-based care for their child's asthma, over 12 months.

Study Schedule

Data on child and parent outcomes will be collected in-person at enrollment and by telephone interviews at 3, 6, and 12 months post-enrollment. These telephone interviews will all be coordinated and conducted by the Seattle Children's study staff. Given the highly seasonal nature of asthma-related morbidity, the text message component of the intervention will continue for 12 months (3 months of biweekly educational interactive text messages; ongoing parent-initiated access to key messages and reminder text messages for PCP follow-up/medication refills/annual flu vaccines) allowing for the capture of individual variability in disease course. (Figure 3).

[figure not shown]

Figure 3

Study Population

The study population will be parents/guardians of Medicaid- insured patients seen in the Seattle Children’s or Mary Bridge Children’s ED for treatment of their asthma. These are patients whose asthma is not yet well controlled and who experience the greatest morbidity due to environmental and social factors and are thus the most resource-intensive group.

Inclusion criteria: Parents of Medicaid-insured children age 2 to 12 years inclusive with physician- diagnosed asthma for at least 12 months will be eligible. Older children/adolescents are excluded because they assume greater responsibility for asthma self-management, and their communication with providers becomes more independent over time. Parents must be

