the primary owners of a mobile phone with text messaging service, which is anticipated to be at least 75% of parents in this population based on previous research on urban, low-income parents.^{59, 60}

Exclusion criteria: Parents of children with significant medical co-morbidities (e.g., sickle cell disease, insulin-dependent diabetes mellitus) will be excluded because of their increased interaction with healthcare providers.

Recruitment and Randomization

CRA's will identify potentially eligible patients through electronic admission board and medical record diagnostic codes after intake into the ED, and they will describe the study to potentially eligible parents while they are waiting to be seen by a provider. Interested families will be screened for eligibility. If eligible, parents will complete the consent process. (See section 5.2.a for more details.) Then the CRA will administer a baseline questionnaire focusing on health care utilization, asthma self-management and morbidity, parental self-efficacy and outcome expectations. After the questionnaire is completed, participants will be randomized to usual care or the intervention group (T2B). Randomization will occur automatically via the RedCap database system. Time allowing, participants randomized to the intervention will receive brief education on the 3 S's and orientation to the text message component (including an "opt-in" code) while in the ED or if necessary by phone within 48 hours. The text message education component will begin within 1 week after participants are randomized, allowing time for participants to enter the opt-in code.

Retention and Compensation

Parents will receive total compensation of \$110 for participation in the study to be dispensed as: \$20 gift card will be given to the parent after he/she completes the baseline interview and \$30 gift cards will be sent after the 3, 6, 12 follow-up interviews; Based on previous studies conducted by our research team with similar populations, this amount should be sufficient to compensate participants for their time and offset the cost incurred for the text messages (if any), but it will not be coercive, minimizing participation solely based on financial gain.

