Trained CRAs will conduct structured in-person interviews after participants have consented and before randomization. Follow-up interviews, lasting approximately 30 minutes, will be conducted by a trained CRA blinded to participants' randomization. In cases when no blinded CRA is available an unblinded CRA may complete the survey. Unblinded status will be documented for each survey conducted. Electronic medical record review will be conducted by trained study staff at the site where the participant was enrolled. Measures of asthma outcomes for this study are aligned with the recent recommendations of the Asthma Outcomes Groups for standardization of definitions and data collection methodologies for asthma research studies and clinical trials.^{75,76} All, but one of the following measures will be administered at each wave of data collection. The Asthma Self-Management Questionnaire will be administered at baseline and 12 months. (see appendix for Baseline Survey).

Distal Outcome Measures – Child Asthma Outcomes

ED visits for asthma care: Parents will report whether and how many times their child was taken to the emergency room because of asthma during the past 12 months using 2 questions administered in several national-scale surveys;⁷⁵ they will also indicate whether those visits included receipt of systemic corticosteroids.⁷⁶ We will validate a large portion of this data with EMR review because Seattle Children's is the primary ED utilized by young patients in the Seattle area and Mary Bridge Children's the primary ED utilized by young patients in the Tacoma area.

Asthma Morbidity: Asthma morbidity will be assessed by the questions used in the Inner City Asthma Consortium (ICAC)^{73, 74, 77, 78} and applied subsequently in numerous studies, including the study validating the IMPACT DC intervention.¹⁵ Morbidity will be measured as the number of days (or nights) of impairment in the prior 2 weeks.

Proximal Outcome Measures – Adherence to Treatment Recommendations

Primary Care Utilization: To maintain continuity in outcomes with the IMPACT DC RCT,¹⁵ we will ask parents to identify their child’s primary asthma health care provider, as well as their child’s primary care provider. A computed variable will indicate whether the named PCP is the child’s primary asthma health care provider. In addition, we will ask parents about frequency of PCP visits for asthma care at each telephone follow-up interview.

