COVER PAGE

Text2Breathe: Enhance Parent Communication to Reduce Pediatric Asthma Disparities (T2B)

NCT03032159

July 10, 2014

C.5. Statistical Analyses

C.5.a: Preliminary Descriptive Analysis of Data

We will summarize all baseline variables overall and by study arm to assess the balance achieved by randomization and to check assumptions such as normality and equality of variances. The distributions of continuous variables will be summarized using means, standard deviations, medians, and ranges. Categorical variables will be summarized using frequency distributions. Non-parametric tests (e.g., Wilcoxon rank-sum and Fisher's exact) will be used in subsequent analyses as needed. Cronbach alpha reliabilities will be estimated for 12 all standardized instruments to assess whether the instruments are as reliable in our target population as in the population on which the instruments were validated. Frequency of missing data for each outcome variable will be determined at each time point. Baseline characteristics of missing and non-missing respondents at the 3, 6, 12 and 24 month time points will be compared to assess for attrition bias. We will employ multiple imputation to account for missing data, if necessary.^{84, 85} We will examine counts of mobile interactions captured by Rip Road (e.g., number of messages received and sent by each participant; See section 5.1.d.) to assess engagement with the intervention, overall and by participant characteristics.

C.5.b: Analysis Plan for Addressing Specific Aims

In **Aim 1**, to assess the intervention effect on the primary and secondary distal outcomes (i.e., the number of ED visits for asthma care during the 12-month interval following randomization, and the number of days of impairment during the two weeks prior to the 12-month interview, respectively), we will utilize negative binomial regression, a generalization of Poisson regression which yields unbiased inference even if the outcome variable is over-dispersed (i.e., the variance exceeds the mean) to estimate incidence rate ratios (IRRs) and 95% confidence intervals (CIs) for count data. The single independent variable in each model will be study group, and the exponentiated form of its regression coefficient will reflect the relative difference between groups in the annual rate of ED visits or frequency of impaired days.

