In **Aim 2**, we will implement a negative binomial regression model to estimate the IRR and 95% CI for number of follow-up visits with the PCP for asthma care over 12 months in the intervention group compared to the usual care group. In addition to the group variable, the model will include a covariate to account for PCP visit frequency prior to randomization. The exponentiated form of the coefficient of the group term will reflect the relative difference between groups in annual rate of PCP follow-up visits for asthma care. We will use linear regression models to examine the intervention effect on knowledge of self-management (continuous scale score). The model independent variables will include study group and pre-randomization level of knowledge of self-management. The magnitude of the group coefficient will provide an estimate of the size and direction of difference between groups controlling for differences in pre-randomization levels.

We will also assess whether primary care utilization (annual rate of follow-up visits) and increased knowledge of self-management mediate the relationship between the assigned communication intervention and child asthma outcomes (defined as frequency of ED and urgent care visits for asthma care and days of impairment). To do so, we will use path analysis models at baseline and each follow-up time separately. To test these hypotheses using longitudinal data, growth trajectories of each outcome will be modeled using multi-process latent growth models (LGM) of these

proximal and distal outcomes. The hypothesized mediating effects of the proximal outcomes will be tested by relating the intervention condition, the latent slope growth factors of the multiple growth processes, and the distal outcomes.⁸⁶

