In prior studies, we have been able to maintain a 90% retention rate over a 6-month follow-up period. We will employ retention strategies that have been successful in this population in previous studies. Conservatively estimating a retention rate of 80% at the 12-month assessment, we must enroll 138 participants in each group (total N=276). The Seattle Children's ED currently serves approximately 1400 2-12 year old asthma patients per year, 40% (n=530) of whom are Medicaid insured. We estimate that 70% of this total will meet the remaining eligibility criteria (n=371). If 40% of these patients consent to the trial, which is much less than the 60-70% participation rates for Seattle Children's ED-based studies, we will yield our projected sample size of 276 in the proposed 24 month enrollment period. Thus, we estimate that we will need to approach 5-7 parents to recruit at least 3 participants per week, with an estimated recruitment of approximately 12 participants per month (minimum of 6 and maximum of 18 in any given month to assure there is not seasonal over-representation in the study sample).

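### The protocol recruits at two EDs, but the SAP was written for one and its Aim 1 models omit enrolling site: a modest loss of precision that one covariate would recover

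*Protocol*

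**What the plan says.** **Sites.** The protocol (Study Design) takes parents of children "seen in the Seattle Children's or Mary Bridge Children's ED". Its Data Collection section treats Seattle Children's as the main ED for Seattle and describes Mary Bridge as "the primary ED utilized by young patients in the Tacoma area". The SAP, dated almost three years before Protocol Version 6, builds its recruitment forecast (C.5.c) on a single hospital, whose "ED currently serves approximately 1400 2-12 year old asthma patients per year". It names no second ED.

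**Allocation.** Protocol, Recruitment and Randomization: "Randomization will occur automatically via the RedCap database system". No strata or block sizes are given.

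**Analysis.** For ED visits and for days of impairment the SAP (C.5.b) says "we will utilize negative binomial regression, a generalization of Poisson regression", and then "The single independent variable in each model will be study group". The Aim 2 count model goes one step further, since "the model will include a covariate to account for PCP visit frequency prior to randomization", but it has no site term either. The linear models for Aims 2 and 3 adjust at most for the pre-randomisation level. Race/ethnicity is the only moderator named. Baseline variables are tabulated by arm "to assess the balance achieved by randomization" (C.5.a), and no analysis depends on what that table shows.

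**The concern.** Enrolling site could plausibly predict the primary outcome. The comparator is standard ED-based care, which the enrolling ED provides. The two EDs draw on different populations. The brief face-to-face education is given in the ED when time allows and otherwise by telephone, so delivery may depend on local conditions. Review of medical records, which checks the parent-reported ED visits, is done by staff at the enrolling site.

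If visit rates differ by site, a model with study group alone has two small costs. A chance excess of one site in one arm moves the estimated IRR, and between-site variation widens the confidence interval. A difference in the IRR between sites would also go unreported, because nothing is shown by site. The SAP's silence looks like the result of its date rather than a considered choice.

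**Working it through.** **Inputs.** From SAP C.5.c: 138 enrolled and 110 analysed per arm, 1.28 visits per year under usual care, a 35% reduction (IRR 0.65, so 0.832 visits), two-sided 5%. Not in the documents, hence assumed: the Mary Bridge share p (30%, range 20-50%), the between-site ratio of ED-visit rates R (1.3, 1.5, 2.0), and the negative binomial dispersion k.

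**1. The plan's own figures.** With a Wald test on the log rate ratio,
n per arm = (1.960 + 1.282)² × (1/1.28 + 1/0.832 + 2k) / (ln 0.65)².
With k = 0 this is 10.507 × 1.983 / 0.1856 = 112.3, so 113. The stated 125 for 90% power follows if k = 0.112, a value the SAP does not give. Enrolment reproduces: 110 / 0.80 = 137.5, so 138 per arm. Site plays no part in these figures, and the fix does not change them.

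**2. Chance imbalance in site mix under simple randomisation.**
SD of the between-arm difference in share = √(2p(1−p)/n) = √(2 × 0.3 × 0.7 / 138) = 0.0552.
95% bound: d = 1.96 × 0.0552 = 0.108. Median absolute difference: d = 0.6745 × 0.0552 = 0.037.

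**3. Effect on the IRR.** The unadjusted IRR is multiplied by
F = [1 + (p + d/2)(R − 1)] / [1 + (p − d/2)(R − 1)].
For R = 1.5 at the 95% bound, F = (1 + 0.354 × 0.5) / (1 + 0.246 × 0.5) = 1.177 / 1.123 = 1.048.

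| R | F at the median difference | F at the 95% bound |
|---|---|---|
| 1.3 | 1.010 | 1.030 |
| 1.5 | 1.016 | 1.048 |
| 2.0 | 1.029 | 1.087 |

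Over shares of 20-50% the 95% bound runs from 1.027 to 1.087.

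**4. The same with 110 analysed per arm.** The SD is √(0.42/110) = 0.0618 and the 95% bound is d = 0.121. F is 1.054 at R = 1.5 and 1.098 at R = 2.0, so at that bound a true IRR of 0.65 would read 0.617 or 0.685 (R = 1.5), and 0.592 or 0.714 (R = 2.0). With k = 0.112 the standard error of the log IRR is √((1/1.28 + 1/0.832 + 0.224)/110) = 0.142. The shifts are then ln(1.054)/0.142 = 0.37 and ln(1.098)/0.142 = 0.66 standard errors. For p of 10-50% and R of 1.25-2.0, the factor at this bound is 1.02-1.10.

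**5. Simulation.** 4,000 trials per setting, 110 per arm, p = 30%, k = 0.112, true IRR 0.65. Power:

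| R | Allocation | Group only | Group + site |
|---|---|---|---|
| 1.5 | simple | 85.5% | 86.6% |
| 1.5 | stratified by site | 86.0% | 86.8% |
| 2.0 | simple | 81.5% | 85.1% |
| 2.0 | stratified by site | 82.9% | 85.1% |

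The mean IRR lay between 0.648 and 0.652 in every cell. With a true IRR of 1, rejection rates were 4.3-5.4% for group only and 4.9-5.8% with site. The Monte Carlo standard error of a power near 85% is √(0.85 × 0.15 / 4000) = 0.6 points, so the gain at R = 1.5 (86.8 − 85.5 = 1.3 points) is close to simulation noise. The gain at R = 2.0 (85.1 − 81.5 = 3.6 points) is clear. Almost all of it comes from the site term; stratification adds little once site is in the model.

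**The case against.** The strongest reply is that this is not a validity problem. Any prognostic variable left out of a randomised comparison passes its chance imbalance into the estimate, and the confidence interval already allows for that. This stands: the unadjusted estimate stayed centred and type I error stayed near 5%. For scale, even with Poisson variation the 95% interval at 110 per arm spans a factor of exp(1.96 × √(1.983/110)) = 1.30 either way.

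Three stronger readings are tempting, and the documents do not support them.

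- A reader might infer that allocation was unstratified and site therefore unbalanced. The protocol is silent, which shows only that stratification is not stated. REDCap may have been set up with site strata, and the SAP begins at C.5 and refers to sections not included. Even simple randomisation balances site in expectation.
- A reader might infer that different research assistants deliver the education at each hospital. No section says who delivers it.
- A reader might infer that the primary outcome is ascertained differently by site. The protocol (Study Schedule) has Seattle Children's staff coordinate and conduct all follow-up telephone interviews, and ED visits are parent-reported. Record review is local, but it is described as validating those reports. It would affect the IRR only if record counts replaced them, which the documents do not say.

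Two further points stand in part. Some of any site difference in ED use would be captured by adjusting for each child's earlier ED visits, though the Aim 1 models do not do that either. And if site is tabulated in the baseline table, an imbalance would be visible there, but the SAP says nothing about acting on it.

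**Conclusion.** The point holds as a low-cost improvement in precision and a needed update, not as a flaw that threatens the result. The protocol describes two EDs and the SAP one, and the Aim 1 models exclude enrolling site by an explicit rule. With a 30% Mary Bridge share, 138 per arm, simple randomisation and site rate ratios of 1.3-2.0, chance imbalance would typically move the primary IRR by about 1-3%, and by about 3-9% at the 95% bound. Stratification plus a site term would gain roughly 1-4 points of power at ratios of 1.5-2.0. Both the share and the ratio are assumptions, and if the sites have similar rates the effect is close to nil. If allocation was in fact stratified by site, the imbalance largely disappears and the case for the site term rests on precision alone.

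A reader might conclude that the planned primary analysis is biased or its p-value unsafe. Neither the documents nor the calculations support that. With a log link and randomised allocation, adding site also leaves the target rate ratio unchanged, provided the effect is the same at both sites.

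**What to change.** 1. Update the SAP to two sites, and say whether the 1.28 visits per year, taken from 2012 ED records, is meant to apply to both EDs.
2. In SAP C.5.b, replace the single-variable rule for Aim 1 with, for example: *Each Aim 1 outcome will be analysed by negative binomial regression with study group and enrolling site (Seattle Children's, Mary Bridge) as fixed factors.* Add site to the Aim 2 and Aim 3 group-comparison models as well.
3. Show the primary IRR by site, as description only.
4. In the protocol's Recruitment and Randomization section, state whether REDCap allocation is stratified by site. If it is not and enrolment continues, stratify the remaining allocations by site in permuted blocks. The site term covers participants already allocated.
5. If outcomes by arm have already been seen, keep the unadjusted model as primary and report the site-adjusted model as a labelled sensitivity analysis.

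Cost: one degree of freedom per model, a revised SAP and, only if item 4 requires it, a new allocation table in REDCap. No extra participants, visits or data are needed, since the enrolling site is already known for each family.
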